3.2.3 Exclusion Criteria for All Cohorts

Patients who meet ANY of the following criteria will be excluded from study entry.

1. Untreated brain metastases.
2. A patient who has had prior immune therapy or chemotherapy within 4 weeks prior to study Day 1, or who has not recovered (i.e., \leq Grade 1 or at baseline) from adverse events due to a previously administered agent will be excluded. Patients who have had prior molecular targeted therapy using small molecule inhibitors must have received their last dose no less than 2 weeks prior to or no less than five half-lives from study Day 1.
 - a. Note: If subject received major surgery, they must have recovered adequately from the toxicity and/or complications from the intervention prior to starting therapy.
 - b. Note: Toxicity that has not recovered to \leq Grade 1 is allowed if it meets the inclusion requirements for laboratory parameters.
3. Has had prior treatment with any other CSF1R inhibitor or CD40 agonist.
4. Use of corticosteroids to control immune related adverse events at enrollment will not be allowed, and patients who previously required corticosteroids for symptom control must be off steroids for at least 2 weeks. Low-dose steroid use (\leq 10 mg of prednisone or equivalent) as corticosteroid replacement therapy for primary or secondary adrenal insufficiency is allowed.
5. Has not recovered (i.e., \leq Grade 1 or at baseline) from adverse events due to prior treatments with the exception of clinically insignificant adverse events such as alopecia, clinically insignificant laboratory abnormalities, clinically insignificant rash and Grade 2 neuropathy.
6. History of grade 3-4 neurologic or cardiac toxicity or life-threatening liver toxicity poorly responsive to steroids with prior anti-PD-1/anti-PDL1 monotherapy.
7. Presence of leptomeningeal disease.
8. Has active autoimmune disease unrelated to immune checkpoint inhibitors that has required systemic treatment in the past year (i.e. with use of disease modifying agents, corticosteroids or immunosuppressive drugs). Replacement therapy (eg., thyroxine, insulin, or physiologic corticosteroid replacement therapy for adrenal or pituitary insufficiency, etc.) is not considered a form of systemic treatment.
9. Pregnancy or breast feeding. Should a woman become pregnant or suspect she is pregnant while participating in this study, she should inform her treating physician immediately. Because there is an unknown but potential risk for adverse events in nursing infants secondary to treatment of the mother with nivolumab, cabirizumab or APX005M, breastfeeding must be discontinued if the mother is enrolled on this trial.
10. Patients may not be receiving any other investigational agents and may not have participated in a study of an investigational agent or using an investigational device within 4 weeks of the first dose of treatment.
11. Patients with either a concurrent medical condition (including medical illness, such as active infection requiring treatment with intravenous antibiotics or the presence of laboratory

abnormalities) or history of a prior condition that places the patient at unacceptable risk if he/she were treated with the study drug or a medical condition that confounds the ability to interpret data from the study.

12. Concurrent, active malignancies in addition to those being studied (other than cutaneous squamous cell carcinoma or basal cell carcinoma)
13. Active (non-infectious) pneumonitis.
14. Has a known Human Immunodeficiency Virus (HIV), Hepatitis B (HBV), or Hepatitis C (HCV) acute or chronic infection.
15. Has received a live vaccine within 30 days prior to the first dose of trial treatment.
16. History of myocardial infarction or unstable angina within 3 months prior to Cycle 1, Day 1
17. Prisoners, or subjects who are under compulsory detention
18. Current or history of clinically significant muscle disorders (e.g., myositis), recent unresolved muscle injury, or any condition known to elevate serum CK levels
19. History of anti-drug antibodies, severe allergic, anaphylactic, or other infusion-related reaction to a previous biologic agent
20. Concomitant use of statins on study. However, a patient using statins for over 3 months prior to study drug administration and in stable status without CK rise may be permitted to enroll
21. Open wounds and active skin infections
22. Uveal melanoma in the Phase Ib dose expansion trial

3.2.4 Women of Childbearing Potential

Women of childbearing potential (WOCBP) include any females who have experienced menarche and who have not undergone surgical sterilization (hysterectomy, bilateral tubal ligation, or bilateral oophorectomy), and who are not post-menopausal. Post-menopause is defined as:

- Amenorrhea ≥ 12 consecutive months without another cause, and a documented serum follicle stimulating hormone (FSH) level >35 mIU/mL, *or*
- Women with irregular menstrual periods and a documented serum FSH level >35 mIU/mL (*Note*: FSH level testing is not required for women ≥ 62 years old with amenorrhea of ≥ 1 year), *or*
- Women on hormone replacement therapy (HRT).

Women who are using oral or other hormonal contraceptives, such as vaginal products, skin patches, or implanted or injectable products, or mechanical products, such as an intrauterine

device or barrier methods (diaphragm, condoms, spermicides) to prevent pregnancy or who are practicing abstinence or who have a sterile (e.g., vasectomy) partner should be considered to be of childbearing potential [79, 80].

3.3 Concomitant Medications

All medications taken within 28 days before the administration of the first dose of any study drug and all concomitant therapy administered during the study until 100 (± 7) days after last dose of any study drug (or until initiation of subsequent anti-cancer therapy) will be collected. All subsequent anti-cancer therapy will be collected in the Long-Term Follow-up Period.

Information on all prior treatments indicated for advanced cancer, including chemotherapy, biochemotherapy, immunotherapy, radiation, surgery, biologic, and experimental therapy will be collected.

No concomitant medication information will be collected following patient discontinuation from the study except for concomitant medication use associated with study drug-related AEs or AEs that lead to discontinuation from the study.

3.3.1 Prohibited and/or Restricted Treatments

The following medications are prohibited during the study (unless utilized to treat a drug-related AE or specified in the eligibility section):

- Immunosuppressive agents
- Immunosuppressive doses of systemic corticosteroids
- Vaccines except as noted in Section 3.3.2
- Statins for treatment of hypercholesterolemia. Statins will be allowed only if the patient is on a stable dose for over 3 months prior to the study and has a stable status without any CK elevations
- Other therapies including biologic, immunotherapy, extensive non-palliative radiation therapy, standard treatments, or investigational agents or devices

3.3.2 Permitted Therapy

Patients are permitted to use of topical, ocular, intra-articular, intranasal, and inhaled corticosteroids (with minimal systemic absorption). Adrenal replacement steroid doses >10 mg daily prednisone are permitted. A brief (less than 3 weeks) course of corticosteroids for prophylaxis (e.g., contrast dye allergy) or for treatment of non-autoimmune conditions (e.g., delayed-type hypersensitivity reaction caused by a contact allergen) and also for the treatment of tumor-related AE is permitted.

Concomitant palliative and supportive care for disease-related symptoms (including bisphosphonates and RANK-L inhibitors) is allowed. Transfusions are permitted as needed.

The inactivated seasonal influenza vaccine can be given to patients while on therapy without restriction. Influenza vaccines containing live virus or other clinically indicated vaccinations for infectious diseases (i.e., pneumovax, varicella, etc.) must be discussed with the Investigators and Industry Collaborators. In general, live vaccines are prohibited within 30 days prior to start of study drugs and within the first 12 cycles on study.

Palliative radiation or metastasectomy is allowed; these lesions will be subsequently be included for tumor measurements.

Concomitant use of statins will be allowed only if the patient is on a stable dose for over 3 months prior to the study and is in stable status without any CK elevations.

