3.1.6.2 Treatment Beyond Progression

Accumulating clinical evidence indicates that the emergence of objective responses to agents that activate anti-tumor immune responses may follow delayed kinetics of weeks or months, and can be preceded by initial apparent progression of disease with the appearance of new lesions or some enlarging of lesions while certain index lesions are regressing (“mixed response”). Therefore, it is reasonable to allow patients who experience apparent progression to continue to receive treatment until progression is confirmed at the next imaging assessment. These considerations should be balanced by clinical judgment as to whether the patient is clinically deteriorating and unlikely to receive any benefit from continued treatment.

Such deterioration will be assessed to have occurred after a clinical event that, in the Investigator’s opinion, is attributable to disease progression and is unlikely to reverse with continued study treatment and therefore indicates that the patient is not benefiting from study treatment and cannot be managed by the addition of supportive care. The decision to continue treatment should be discussed with the PI.

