 - a. Tumor sites situated in a previously irradiated area, or in an area subjected to other loco-regional therapy, are not considered measurable unless there has been demonstrated progression in the lesion.
15. Prior focal radiotherapy must be completed before first dose of study drug administration, although palliative radiation may be allowed on treatment (see permitted concomitant therapies below). Radiation to pulmonary or intestinal sites must be completed at least 4 weeks prior to study Day 1. There is no time restriction prior to study Day 1 for patients who have received radiation to bone, soft tissue sites or other sites. No radiopharmaceuticals (strontium, samarium) within 8 weeks before first dose of study drug administration.
16. Major surgery must be completed at least 4 weeks before first dose of study drug administration. Surgery requiring local/epidural anesthesia must be completed at least 72 hours before first dose of study drug administration and patients should have recovered. Surgical wounds must be healed.

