5.2.3 Long-Term Follow-up for All Patients

Patients should continue onto Long-Term Follow-up after completing the End-of-Treatment Follow-up Period.

Patients will be followed every 12 (± 2) weeks for survival. Patients who discontinue treatment while showing clinical benefit (complete response [CR], partial response [PR], or stable disease [SD]) should have tumor assessments during these visits for duration of response.

Long-Term Follow-up for survival may be conducted by telephone, rather than by an in-person visit, once tumor progression is determined or use of subsequent anti-cancer therapy has been initiated.

During the Long-Term Follow-up Period, if the patient undergoes local therapy (e.g., resection, radiation) or new systemic therapy is initiated, this should be documented. Patients should be followed until death, loss to follow-up, withdrawal of consent, or study termination by the Sponsor.

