5.3.2 Efficacy Assessments

5.3.2.1 Primary Efficacy Parameters

The primary efficacy parameter is the objective response rate (ORR; number of patients with confirmed response of CR or PR, divided by the total number of treated patients who are

evaluable for a response). Tumor response status will be assessed using RECIST v1.1 by investigator review.

Board-certified radiologists will determine radiographic response and/or progression following enrollment in according to RECIST v1.1.

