5.3.2.1.1 Tumor Assessment

Tumor assessments will be performed at Screening (within 28 days prior to first dose), then every 8 weeks (\pm 7 days) for a total of 2 sets of imaging studies, followed by every 12 weeks (\pm 7 days) thereafter. Imaging will include an initial MRI of the brain with and without contrast as well as body imaging with either PET CT, CT scans, or MRI. If an MRI of the brain is contraindicated, a head CT with and without contrast should be performed. Brain imaging can be performed every 6 months unless clinically indicated in shorter intervals, such as in patients with metastatic melanoma. All patients should have tumor response parameters assessed at the End-of-Treatment visit unless a tumor assessment has been performed within 8 weeks prior to an End-of-Treatment Visit or if tumor progression was previously determined. Patients who enter Long-Term Follow-up while showing clinical benefit should have tumor assessments every 12 weeks (\pm 7 days) for duration of response. The same measuring modality should be preferably used by the site to maintain consistency across the study.

Response will be evaluated using RECIST v1.1.

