5.3.2.3 Tumor Biopsy for Fresh Tumor Tissue Collection

Biopsy at the primary tumor site or metastatic site will be collected prior to Cycle 1 Day 1 and on-treatment (within 7 days prior to Cycle 5, Day 1, and at least 24 hours prior to dosing) for all patients. Patients may also have on-treatment biopsy upon documented tumor response and post-treatment biopsy upon documented tumor progression, as deemed safe and accessible by the Investigator (Appendix E). If available, tumor tissue obtained from post-treatment procedures such as surgery may also be collected.

Biopsied lesions may become inflamed, bleed, or change dimensions, which could result in inaccurate tumor measurements. Therefore, it is recommended not to use the biopsied lesion as a target lesion when assessing the response by RECIST v 1.1 criteria when possible.

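### Section 3.3.2 puts lesions irradiated or resected on study into the tumor measurements without condition, and no efficacy section says how they count in the primary ORR

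*Combined protocol and SAP*

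**What the plan says.** On-study local therapy is allowed. Criterion 15 in section 3.2.2 points to it ("although palliative radiation may be allowed on treatment (see permitted concomitant therapies below"), and section 3.3.2 states: "Palliative radiation or metastasectomy is allowed; these lesions will be subsequently be included for tumor measurements". No condition is attached, such as progression of the treated lesion.

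The primary efficacy parameter in Phase 1b is the ORR. Section 5.3.2.1 counts confirmed CR or PR and says: "Tumor response status will be assessed using RECIST v1.1 by investigator review". Section 5.3.2.1.1 gives the scan schedule and closes with: "Response will be evaluated using RECIST v1.1". Section 7.3 defines the ORR through a best overall response of CR or PR among evaluable patients. None of these, nor section 5.3.2.2, mentions a lesion irradiated or resected during the study.

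Two nearby rules deal with related situations. Criterion 14a, which sits under the requirement for a measurable lesion at baseline, says that sites previously irradiated or "in an area subjected to other loco-regional therapy, are not considered measurable unless there has been demonstrated progression in the lesion". Section 5.3.2.3 warns: "Biopsied lesions may become inflamed, bleed, or change dimensions, which could result in inaccurate tumor measurements". It goes on to recommend against using such lesions as targets where possible. For long-term follow-up, section 5.2.3 asks only for a record: "if the patient undergoes local therapy (e.g., resection, radiation) or new systemic therapy is initiated, this should be documented".

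**The concern.** A resected lesion has no tumor left to measure, and an irradiated lesion may shrink because of the radiation. If either stays in the tumor measurements without qualification, part of a recorded response may be due to local therapy and not to the three study drugs. There is no control arm in which such an effect would cancel.

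Each disease cohort is judged on a small count, so a single misattributed response can matter at either limit. Two readers could also classify the same patient differently, one following section 3.3.2 and the other following whatever RECIST v1.1 provides. The plan does not say which text prevails.

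**Working it through.** **Step 1. The texts side by side.**

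- Section 3.3.2 covers lesions given palliative radiation or metastasectomy on study. It directs inclusion, without condition.
- Criterion 14a covers sites treated before baseline. It calls them not measurable unless the lesion has progressed.
- Section 5.3.2.3 covers biopsied lesions. It warns of inaccurate measurement and advises against target status where possible.
- Sections 5.3.2.1, 5.3.2.1.1, 5.3.2.2 and 7.3 name RECIST v1.1 or define the endpoint. They give no rule for lesions treated on study.

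Only section 3.3.2 addresses the lesions in question. Criterion 14a and section 5.3.2.3 apply by analogy: they show that the protocol elsewhere recognizes that an intervention on a lesion can spoil its measurement.

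**Step 2. Reproducing the stated design.** The inputs from section 7.1 are a null rate of 10%, an alternative of 25%, 13 patients in stage 1 with a stop at 1 or fewer responses, 21 more patients, and rejection at 6 or more of 34. The stated type I error is 0.1 and the stated power is 80%.

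With X ~ Bin(13, p) and Y ~ Bin(21, p):

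P(reject) = Σ over x = 2 to 13 of P(X = x) · P(Y ≥ 6 − x)

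At p = 0.10:

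- x = 2: 0.2448 × 0.1520 = 0.0372
- x = 3: 0.0997 × 0.3516 = 0.0351
- x = 4: 0.0277 × 0.6353 = 0.0176
- x = 5: 0.0055 × 0.8906 = 0.0049
- x ≥ 6: 0.0009

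The sum is 0.0957. At p = 0.25 the same formula gives 0.8108. The stated design is reproduced, with little slack below 0.1.

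**Step 3. Sensitivity to falsely counted responses.** Suppose a share q of true non-responders is counted as CR or PR because of local therapy. The apparent response rate at a true 10% is p = 0.10 + 0.90 × q. The values of q are assumptions; the documents give none.

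| Assumed q | Apparent rate | Expected false responses per 34 patients (30.6 × q) | Type I error | Increase |
|---|---|---|---|---|
| 0 | 0.1000 | 0 | 0.096 | – |
| 0.5% | 0.1045 | 0.15 | 0.112 | 0.016 |
| 1% | 0.1090 | 0.31 | 0.130 | 0.034 |
| 2% | 0.1180 | 0.61 | 0.169 | 0.073 |

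Here 30.6 = 34 × 0.90 is the expected number of non-responders in a full cohort at the null. Even q = 0.5% takes the error above 0.1. At the first look, the chance of exactly 1 response in 13 at a true 10% is 0.367. In such a cohort one further counted response would turn a stop into a continuation.

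**The case against.** The strongest reply is that RECIST v1.1 governs response and that, under section 5.3.2.1, board-certified radiologists determine it. Being included in measurements is not the same as being credited as response. Inclusion can even be conservative, since a treated lesion that regrows would still count toward progression. This stands in part: the documents do not reproduce RECIST v1.1, so whether it would override section 3.3.2 cannot be checked from them. But the protocol's only specific sentence on these lesions directs inclusion, and nothing ranks the two texts.

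Second, the pathway is narrow. Section 3.3.1 prohibits extensive non-palliative radiation, and section 4.11 lists documented progression and a need for alternative therapy as grounds for stopping treatment. A false response needs a treated lesion that drives the response, no progression elsewhere, and confirmation. This stands, and it is why the effect may be near zero. Confirmation does not close the gap, because a resected lesion is still absent at the next scan.

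Third, the doubled verb suggests a slip. That may be so, but the documents do not show what was meant, so the sentence needs correction either way.

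A reader might infer that section 3.3.2 flatly contradicts criterion 14a. The documents do not support that. Criterion 14a governs measurability at baseline for eligibility, not lesions treated later, so it gives an analogy and no opposing rule.

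**Conclusion.** The defect holds as a matter of text. Section 3.3.2 gives an unconditional inclusion rule for lesions irradiated or resected on study, and the sections that define the primary endpoint neither qualify nor replace it. It should be fixed because it bears on the primary ORR in single-arm cohorts with low decision limits.

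A reader might go further and infer that type I error in this trial is inflated to 0.112, 0.130 or 0.169. The documents do not support that. Those figures rest on assumed false-response rates of 0.5%, 1% and 2%, and on readers crediting local-therapy shrinkage as response. With no stated frequency of on-study local therapy, the true size is unknown and possibly near zero. The figures show only that the design has little room: its exact error is 0.096 against a stated 0.1.

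**What to change.** Correct the sentence in section 3.3.2 so that its meaning is clear. Then state in sections 5.3.2.1.1 and 7.3, for the primary ORR, that:

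- a decrease or disappearance of a lesion after on-study radiation or resection cannot by itself establish CR or PR;
- growth of such a lesion still counts toward progression;
- responses confirmed before local therapy stand;
- later responses in untreated lesions can still count, in keeping with section 3.1.6.2, which expects that responses "may follow delayed kinetics of weeks or months";
- patients with local therapy and no qualifying response stay in the denominator as non-responders.

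Add one sensitivity analysis that uses only assessments made before local therapy. It should not be the primary rule, because it would discard genuine late responses. If an assumed 2% of true responders were lost that way, the rate would be 0.25 × 0.98 = 0.245 and exact power would fall from 0.811 to 0.796, below the stated 80%.

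The cost is a few sentences of wording and one extra analysis. The downside is a possibly slightly lower ORR. Permission to give palliative radiation or metastasectomy does not change.

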3.4 Long-Term Follow-up

Patients who discontinue treatment while still receiving clinical benefit (i.e., CR, PR or SD) should get follow-up tumor scans every 12 (± 2) weeks until disease progression or use of subsequent anti-cancer therapy to determine the duration of response, unless consent is withdrawn.

Long-Term Follow-up for survival may be conducted by telephone, rather than by an in-person visit, once tumor progression is determined or use of subsequent anti-cancer therapy has been initiated.

4. Study Drugs

In this study, APX005M, cabiralizumab and nivolumab, are considered Investigational Medicinal Products (IMP).

4.1 Investigational Products

An investigational product, also known as investigational medicinal product in some regions, is defined as a pharmaceutical form of an active substance or placebo being tested or used as a reference in a clinical study, including products already having a marketing authorization but used or assembled (formulated or packaged) differently than the authorized form, or used for an unauthorized indication, or when used to gain further information about the authorized form. In this protocol, the investigational products are APX005M, cabiralizumab and nivolumab.

Please refer to the Pharmacy Manual and/or Investigator's brochures for more specific information on each drug product.

Table 4 Study treatments				
Product Description / Class and Dosage Form	Potency/Route of Administration	Blinded or Open Label	Packaging / Appearance	Storage Conditions (Per Label)
Nivolumab (BMS-936558-01) Solution for Injection	100 mg (10 mg/mL)	Open label	Vial	Refer to the label on container and/or pharmacy manual
Nivolumab (BMS-936558-01) Solution for Injection	40 mg (10 mg/mL)	Open label	Vial	Refer to the label on container and/or pharmacy manual
Cabiralizumab (BMS-986227) Solution for Injection	140 mg (20 mg/mL)	Open label	Vial	Refer to the label on container and/or pharmacy manual
APX005M Solution for Injection	200 mg (10 mg/mL)	Open label	Vial	Refer to the label on container and/or pharmacy manual

